## 7.2 Determination of Sample Size

The sample size calculation for the LACC trial was based on an expected DFS rate of 90% in the open surgery group at 4.5 years and a non-inferiority margin of -7.2% for the difference in DFS rate at 4.5 years (minimally invasive surgery minus open surgery). In the end, the observed DFS rate in the open surgery group at 4.5 years was 96.5%, which was much higher than the assumed DFS rate of 90%, and the difference in DFS rate at 4.5 years (minimally invasive surgery minus open surgery) was -10.6% (95% confidence interval [CI]: -16.4% to -4.7%). The hazard ratio for DFS was estimated to be 3.74 (95% CI: 1.63 to 8.58). Thus, the non-inferiority of minimally invasive surgery compared to open surgery could not be concluded in the LACC trial.

The G-LACC trial is planned to demonstrate that the negative impact of minimally invasive surgery on DFS in the LACC trial was the consequence of an inappropriate minimally invasive surgical procedure. Based on previous studies and clinical experience, the 4.5 year DFS rate for patients undergoing open surgery is expected to be 94% in the German / European context, which is more in line with the outcome of the LACC trial than the initially assumed 90% DFS rate in the LACC trial. In accordance with the LACC trial, a non-inferiority margin of -7% for the difference in DFS rate at 4.5 years (minimally invasive surgery minus open surgery) is considered to be clinically acceptable and was therefore also used for the G-LACC trial. Assuming exponentially distributed event times, the hazard rate for DFS in the open surgery group is estimated to be 0.0138, and the respective non-inferiority margin for the hazard ratio for DFS (minimally invasive surgery/open surgery) is calculated as 2.3. This margin is much lower than the observed upper limit of the hazard ratio for DFS of 8.58 in the LACC trial. A DMC is implemented for close supervision of the accruing information. If similar trends as observed in the LACC trial would be observed in the G-LACC trial, it is the obligation of the DMC to stop the trial for futility.

Sample size estimation for the G-LACC trial was performed in nQuery Advisor version 9 using the non-inferiority test for two survival curves using Cox regression. The one-sided type I error is set to 2.5% and the aimed power is set to 80%. With an assumed probability of primary endpoint event of 6% (=1-94%) at 4.5 years in both arms and each patient will be followed-up for about 4.5 years, a sample size of 378 patients per arm (756 patients in total) will be required to observe 45 primary endpoint events to declare the non-inferiority of minimally invasive surgery compared to open surgery with a non-inferiority margin of 2.3 for the hazard ratio for DFS. The study is event-driven and can be terminated after 45 primary endpoint events have been observed.

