Therefore, we performed a systematic review and meta-analysis where we not only compared the survival rates of open hysterectomy and laparoscopic hysterectomy, but also the results of risk groups including uterine manipulators and prophylactic vaginal suture. 30 studies fulfilled the inclusion criteria. Five prospective, randomized-control trials were included. Patients were analyzed concerning the surgical approach (open surgery AH, laparoscopic surgery LH).

Additionally, three subgroups were created for the LH group: high risk group (manipulator), intermediate risk group (no manipulator, intracorporal colpotomy) and low risk group (no manipulator, vaginal colpotomy). Regarding OS, the meta-analysis showed a superiority of AH (0.96 [0.93; 0.97]) over the whole LH group. Interestingly, OS was significantly higher in LH low risk (0.96 [0.94; 0.98]) compared to LH intermediate risk group (0.93 [0.91; 0.94]). OS rates were comparable in AH and LH low risk group. DFS was higher in the AH group compared to the LH group in general (0.92 [0.88; 0.95] vs. 0.87 [0.82; 0.91]), whereas the application of protective measures (no uterine manipulator in combination with vaginal colpotomy) was associated with increased DFS in laparoscopy (0.91 [0.91; 0.95]). In conclusion, DFS and OS in laparoscopy appear to be depending on surgical technique. Protective operating techniques result in improved minimal invasive survival and seem to be equivalent to open hysterectomy.

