## 7.1.2 Primary endpoint

The primary endpoint disease-free survival (DFS) will be analyzed according to the intention-to-treat (ITT) principle which includes all patients as randomized. The DFS curves will be estimated using the Kaplan-Meier method. A Cox proportional hazards model adjusted for the stratification factors for the randomization will be used for the comparison of minimally invasive and open surgery. Non-inferiority of minimally invasive as compared to open surgery will be declared if the upper boundary of the two-sided 95% CI for the hazard ratio (minimally invasive / open) is below the predefined non-inferiority margin of 2.3. A sensitivity analysis will be performed according to the per-protocol (PP) principle which includes all randomized patients where surgery has been performed according to the initial randomization. Consistency between results in the ITT and PP analysis is needed to draw meaningful conclusion regarding differences in DFS.

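### The 7-point margin converts to a hazard ratio of 2.25; the protocol rounds it up to 2.3, so at the planned 94% DFS the decision threshold allows a 7.3-point loss

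*Protocol*

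**What the plan says.** Protocol section 7.2 sets the acceptable loss on the absolute scale, as "a non-inferiority margin of -7% for the difference in DFS rate at 4.5 years" (minimally invasive minus open), and plans on the basis that "the 4.5 year DFS rate for patients undergoing open surgery is expected to be 94% in the German / European context". It then converts: "Assuming exponentially distributed event times, the hazard rate for DFS in the open surgery group is estimated to be 0.0138" (per year), and "the respective non-inferiority margin for the hazard ratio for DFS (minimally invasive surgery/open surgery) is calculated as 2.3".

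Section 7.1.1 uses 2.3 to define the null hypothesis. Section 7.1.2 declares non-inferiority if the upper limit of the two-sided 95% CI for the hazard ratio "is below the predefined non-inferiority margin of 2.3". Section 7.2 sizes the trial on the same value, with one-sided alpha 2.5%, 80% power, "With an assumed probability of primary endpoint event of 6% (=1-94%) at 4.5 years in both arms", 378 women per arm and 45 events. The figure 2.3 is repeated in the synopsis and in sections 2.2 and 2.4. No rule refers to the absolute difference once the conversion has been made.

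**The concern.** The clinical judgement in this protocol is the 7-point loss. The hazard ratio is presented as its arithmetical equivalent, not as a margin justified in its own right. If the conversion is loose in the permissive direction, the confirmatory test can pass at a loss slightly larger than the one declared acceptable, and the event target is slightly too small for the correct margin. The trial follows one that found harm from minimally invasive surgery, so the threshold should match the stated limit.

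The conversion also holds at only one open-arm DFS rate. Section 7.2 itself records that the LACC trial planned on 90% and observed 96.5%, so the planning rate may be missed here too.

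**Working it through.** **Inputs** (section 7.2 unless stated): open-arm DFS 94% at 4.5 years; acceptable loss 7 points, so 87% in the minimally invasive arm; exponential times; one-sided alpha 2.5% (z = 1.960); power 80% (z = 0.8416); true HR 1; 6% event probability; 1:1 allocation (section 2.1).

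**1. The protocol's own figures**
- Open-arm hazard: -ln(0.94)/4.5 = 0.01375, which agrees with the stated 0.0138.
- Events at margin 2.3 (Schoenfeld): 4 × (1.960 + 0.8416)² / (ln 2.3)² = 45.3.
- Patients: 45.26/0.06 = 754.3, or 377.1 per arm, which rounds up to 378. Conversely, 756 × 0.06 = 45.4 events.

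So 45 events and 378 per arm reproduce from a margin of 2.3.

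**2. The conversion**
- HR = ln(0.87)/ln(0.94) = 0.13926/0.06188 = 2.251.
- Implied DFS at HR 2.3: 0.94^2.3 = 0.8673, a loss of 7.27 points, or 0.27 beyond the limit.

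**3. Effect on the test.** With 45 events, P(declare non-inferiority) = Φ(√(45/4) × ln(2.3/HR) − 1.960). At HR 2.251, a true loss of exactly 7 points, this is 3.0% instead of 2.5%.

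**4. Effect on size and power**
- Events needed at margin 2.25: 4 × (2.8016)² / (ln 2.25)² = 47.7, so 48.
- Power at margin 2.25, from Φ(√(d/4) × ln 2.25 − 1.960): 77.6% with d = 45 and 80.2% with d = 48.

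**5. Dependence on open-arm DFS.** For open-arm DFS p, the HR equal to 7 points is ln(p − 0.07)/ln(p), and the loss allowed by HR 2.3 is p − p^2.3.

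| Open-arm 4.5-year DFS | HR equal to 7 points | Loss allowed by HR 2.3 |
|---|---|---|
| 89% | 1.70 | 12.5 points |
| 92% | 1.95 | 9.5 points |
| 94% | 2.25 | 7.3 points |
| 95% | 2.49 | 6.1 points |
| 96.5% | 3.11 | 4.4 points |

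The two scales agree at about 94.2%. The 89% is the 4.5-year open-arm figure from the European cohort in section 1.4, the 92% is the sponsor's meta-analysis in the same section (no time point given), and the 96.5% is LACC's observed rate.

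**6. Can 48 events be reached?** I assume uniform accrual of 756 women over 48 months, the planned hazard in both arms and no loss to follow-up.
- If all women are followed until the stop, 45 events arrive near month 78 and 48 near month 81.
- If follow-up ends at 5 years, the total expected is 756 × (1 − 0.94^(5/4.5)) = 50.2 events.
- With 10% lost by year 5, that total falls to about 47.7.

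**The case against.** The strongest reply is that this is rounding, not a wrong calculation. The inputs are whole percentages, 2.251 to one decimal is 2.3, and 2.3 is exactly 7 points at open-arm DFS of about 94.2%, which still reads as 94%. LACC's margin of 7.2 points, which the protocol says it follows, gives ln(0.868)/ln(0.94) = 2.288. The sample size is also consistent with the stated 2.3. All of this stands, and it limits the finding to about 0.3 DFS points and 3 events. It does not remove it: the stated limit is 7 points, the margin is said to be calculated from it, and a non-inferiority margin should not be rounded towards leniency.

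A reader might infer three stronger things that the protocol does not support.

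- **That the threshold is looser than 7 points in general.** It is looser only below about 94.2% open-arm DFS. At LACC's 96.5%, the result the protocol says its 94% lies closer to, HR 2.3 is the stricter rule. The 92% pooled figure has no time point, and its interval (0.88 to 0.95) contains 94%.
- **That the type I error is seriously inflated.** At a true 7-point loss the chance of passing would be about 8% if open-arm DFS were 92%. That is measured against an absolute null the protocol does not test. Its null is HR at or above 2.3, and the rule holds that at 2.5%.
- **That a second, absolute criterion must be met.** Testing a hazard ratio derived at the planning rate is a legitimate design choice, and a fixed 7-point rule has the mirror weakness: it tolerates HR 3.1 at 96.5%. A mandatory co-criterion would also lose power if the trial stops at 45 to 48 events. At month 81 only (81 − 54)/48 = 56% of women could have 4.5 years of follow-up.

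The remark that 2.3 is well below LACC's upper limit of 8.58 is weak support for the margin, since 2.3 lies inside that interval (1.63 to 8.58). It enters neither the calculation nor the rule, so whether to keep it is editorial.

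**Conclusion.** The point holds in limited form. On the protocol's own assumptions the margin is 2.25, and 2.3 is that value rounded in the permissive direction. At 94% open-arm DFS the consequences are a permitted loss of 7.3 instead of 7 points, a 3.0% instead of 2.5% chance of accepting a true 7-point loss, and about 78% power if 45 events are tested against 2.25. These figures rest on exponential times, proportional hazards and the Schoenfeld approximation, which reproduces the protocol's own event count.

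The dependence on open-arm DFS is a separate matter of interpretation. It runs in both directions and calls for reporting, not for a new decision rule. Severity: should fix.

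**What to change.** 1. Replace 2.3 with 2.25 wherever it appears: synopsis, sections 2.2, 2.4, 7.1.1, 7.1.2 and 7.2.
2. Raise the event target from 45 to 48 in the synopsis and sections 2.4, 2.5 and 7.2 (80.2% power). Alternatively, keep 45 events and restate the power as about 78%.
3. Add, as a supportive analysis, the Kaplan-Meier difference in 4.5-year DFS with its 95% CI, read against -7 points. Do not make it a condition for declaring non-inferiority.

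**Cost.** Under uniform accrual and no loss, 48 events take about 3 more months if all women are followed until the stop. The wait is longer if follow-up ends at 5 years: about 50 events are then expected in total, and about 47.7 with 10% loss, so the reserve is thin. No more patients are needed if the 5-year follow-up is achieved. On the protocol's own 4.5-year basis, 48 events correspond to 48/0.06/2 = 400 women per arm. The supportive analysis needs no extra data, but its interval will be wide if the trial stops as soon as the event target is met.

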## 7.3 Interim Analysis

No statistical interim analysis is planned. As the study objective is to demonstrate that both operation techniques are equivalent regarding the primary outcome, it is important that this equivalence can also be assessed in relevant subgroups with adequate precision. A DMC is implemented that will carefully oversee the conduct of the study and if one type of surgery is substantially superior to the other the study needs to be terminated.

#### 8 DATA MANAGEMENT

#### 8.1 Data recording and record keeping

All study data will be collected by the investigator and/or other study personnel. A clinical trial data base is provided, in which the data are entered via an eCRF. Authorized and trained staff of the study sites will enter the data in the eCRF. Serious adverse events will be documented in the eCRF. Verification of the data in the eCRF occurs by monitoring as well as via range, validity and consistency checks programmed in the system. In certain cases, queries can be detected from the study software or from authorized study staff. Based on the queries, the investigator can review and answer the found discrepancies directly in the system. All changes of data entered in the eCRF can be followed by an audit trail. A quality control will be performed before the database is closed. This procedure is documented. Finally, data transfer takes place for statistical evaluation.

The data management plan contains further details about data management processes.

The investigator agrees to keep the trial investigator file (TIF), including the identity of all participating patients, all original signed informed consent forms, detailed records of treatment, all other applicable study-related documents as well as source documents. The records should be retained by the investigator for at least 10 years after termination or premature discontinuation of the clinical study. Source data have to be kept according to national regulations.

## 8.2 Data Protection

All study staff has to give due consideration to data protection and medical confidentiality. The collection, transfer, storage, and analysis of personal study-related data are performed pseudonymized according to national regulations. The investigator must assure that patients' anonymity will be maintained and that their identities are protected from unauthorized parties. The declaration of data protection is contained within the patient information/informed consent form. At any time, participants may withdraw their consent for any reason without any negative consequences regarding their treatment. Information about subjects will be kept confidential and managed in accordance with all applicable privacy laws, rules, and EU General Data Protection Regulation (GDPR). Subject confidentiality and privacy are strictly held in trust by the participating investigators, the study site personnel and responsible investigator. This confidentiality is extended to cover testing of biological samples in addition to the clinical information relating to subjects. Therefore, the study protocol, documentation, data, and all other information generated will be held in strict confidence.

The subject's contact or identifying information will be securely stored at each study site for internal use during the study. After completion or premature termination of the clinical trial, all records will continue to be kept in a secure location for as long as dictated by local regulations.

On CRFs or other documents submitted to the Trial steering committee, patients should not be identified by their names, but by a subject identification number. The investigator should keep a subject enrolment log showing subject identification number, names and addresses. Participating patients will be identified by a study specific subject identification number consisting of two digits for the study site and 3 digits for the subject number within the study site. This subject identification number will be used when registering the patient into the study database. The woman's national identification number will not be entered into the database. The key to the code will be available to the investigator only.

#### 9 QUALITY ASSURANCE

#### 9.1 Trial Steering Committee

A Trial Steering Committee (TSC) will be implemented to provide oversight of the conduct of the trial. This includes the practical aspects of the study as well as ensuring that the study continues to be run in a way which is both safe for the patients and provides appropriate safety and efficacy data to the investigators. In discharging its safety role, the TSC will work in conjunction with the Data Safety Monitoring Board that will also be established for the trial (see section 9.2).

Specific responsibilities of the TSC include, but are not limited to, the following:

- to provide overall supervision of the trial
- to approve the main study protocol and any amendments
- to review, select and train the participating trial sites
- to monitor and supervise the trial towards its objectives and its progress
- to take steps to reduce deviations from the protocol to a minimum
- to review relevant information from other sources
- to consider the recommendations of the DMC

Face-to-face meetings – if not possible then web based – were held at regular intervals determined by need and not less than once a year. Routine business was conducted by telephone, email and post. The TSC will have ultimate responsibility for the trial and will assume primacy over the DMC or responsible investigator. The Trial Steering Committee can prematurely terminate the trial.

## 9.2 Data Monitoring Committee

An independent Data Monitoring Committee (DMC) will be implemented to detect possible harms and to assure continuous risk/benefit assessment. The DMC will be composed of independent experts not involved in the conduct of the trial. Details of the definition of DMC, its composition and its roles and responsibilities can be found in a separate DMC charter.

The DMC will review the data in the context of safety, validity and quality and will carry out the following interim analyses during the course of the trial:

- Evaluation of the study data at least once a year or more often in case of an urgent need e.g. incidence rates of SAEs
- Evaluation of the recruitment rate 3 years after the start of the study (FPI) to ensure the protocol-compliant recruitment after four years

The analyses of the DMC result in one of three recommendations. Thereafter, the DMC may recommend continuing, temporarily halting or early terminating the trial. There commendations will be performed based on blinded data. If the committee determines that it is safe to proceed with the study, the DMC recommendation will remain unknown to everyone except the committee members.

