### **1.6** Risk Benefit Evaluation

The large randomized LACC study demonstrated that MIS is associated with a higher rate of recurrence and death from disease which was confirmed by a recent meta-analysis of observational studies. This is deeply concerning since no clear cause has been established. Most industrialized countries had abandoned the open approach in favor of MIS because of its general advantages with decreased morbidity, less pain, shorter hospital stays and faster recovery. Furthermore, substantial investments in research, education and equipment were triggered in the field of laparoscopic oncologic surgery which led to impressive developments such as fluorescent-guided sentinel techniques. Our sophisticated meta-analysis showed that oncologic outcome in laparoscopy appear to be depending on surgical technique. Protective operating techniques resulted in improved minimal invasive survival and were equivalent to open hysterectomy.

At the moment, a significant number of centers returned back to open surgery, however, others don't. Since MIS is a standard approach in gynecologic surgery, the results of this trial will have a major impact upon national/international guidelines and therefore, on daily clinical practice. The use of nation-wide clinical tumor and quality registers should further improve the oncologic management and constitute a reliable data source for research and quality improvements. The preliminary analyses from the German cancer centers support an advantage of MIS over open surgery, however, this should be interpreted with caution due to its retrospective nature.

Since the LACC trial demonstrated an association between MIS and disease recurrence, the risk for similar outcomes in the G-LACC trial cannot be neglected. However, the potential risk should be balanced against the potential benefits of MIS including less complications, improved quality of life, and future developments within the laparoscopic platforms.

A Data Monitoring Committee (DMC) will be implemented for close supervision of the accruing information, to detect possible harms and to assure continuous risk/benefit assessment. The DMC will review the data in the context of safety, validity and quality on a regular basis and may recommend early termination of the trial in case the DMC observes a significant difference between both treatment groups (see section 7.3 and 9.2).

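### The DMC must act on an outcome difference between arms, including a LACC-like trend against minimally invasive surgery, but section 9.2 bases its recommendations on undefined blinded data

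*Protocol*

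**What the plan says.** Three sections of the protocol give the DMC a task that needs outcomes compared between arms.

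- Section 1.6 (Risk Benefit Evaluation): the DMC "may recommend early termination of the trial in case the DMC observes a significant difference between both treatment groups". It refers the reader to 7.3 and 9.2.
- Section 7.2 (Determination of Sample Size): if trends like those in LACC appear, "it is the obligation of the DMC to stop the trial for futility".
- Section 7.3 (Interim Analysis): "if one type of surgery is substantially superior to the other the study needs to be terminated".

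The two sections named in 1.6 do not supply the means. Section 7.3 says "No statistical interim analysis is planned". Section 9.2 (Data Monitoring Committee) lists a review of the study data at least yearly, with SAE rates as its only example, and a recruitment check after three years. It calls both interim analyses, does not mention DFS by arm, and then says "There commendations will be performed based on blinded data". Composition, roles and responsibilities are left to a separate charter.

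**The concern.** The protocol concedes in 1.6 that LACC-like outcomes could recur, and it offers DMC supervision there and again in 7.2 straight after setting the margin. The duty in 7.2 is directional: a LACC-like trend means that minimally invasive surgery is doing worse. A committee confined to blinded data either cannot see a difference between arms or cannot see which way it runs, depending on what blinded means.

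The trigger is also worded in three ways: a significant difference, substantial superiority of either operation, and a LACC-like trend called futility. A DMC following the protocol would not know which of these applies or what data it may look at. At stake is how early a real excess of recurrences or deaths in one arm would be recognised while women are still being randomised.

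**Working it through.** **Inputs from the protocol.** One-sided type I error 2.5% and power 80% (7.2); margin 2.3 for the hazard ratio (7.2); 6% events at 4.5 years in both arms (7.2); 756 women, 1:1, 48 months of accrual (2.1, 2.5); LACC hazard ratio 3.74 (7.2).

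**Assumptions added here.** Exponential DFS, uniform accrual, no dropout.

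**1. The plan's own figure.** Events = 4 × (1.960 + 0.842)² / (ln 2.3)² = 45.3. Patients = 45.3 / 0.06 = 754, or 378 per arm after rounding up. The 45 events and 756 patients reproduce, so the sample size is not in question here. The control hazard is −ln(0.94) / 4.5 = 0.01375 per year.

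**2. Blinded read as pooled.**
- With 94% DFS in the open arm and hazard ratio 3.74, the minimally invasive arm has 1 − 0.94^3.74 = 20.7% events at 4.5 years.
- The pooled rate is (6.0% + 20.7%) / 2 = 13.3%, or 378 × (0.060 + 0.2066) ≈ 101 events against about 45 planned.
- The same 13.3% arises with no treatment difference if both arms have 86.7% DFS. That is not far-fetched: section 1.4 cites 84% and 88% DFS from the Swedish registry, without giving the time point.
- So pooled data would show an excess over plan but could not attribute it. By arm, the expected share of events under minimally invasive surgery is 3.74 / 4.74 = 79%, against 50% with no difference.

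**3. Blinded read as coded arms.** The DMC would see that one coded arm does worse. That can serve 1.6 and 7.3, which are worded symmetrically. It cannot serve 7.2, which depends on which arm it is.

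**4. What reports by arm would show, and when.** Expected events in an arm by year t (t ≤ 4) = (378/4) × [t − (1 − e^(−λt)) / λ].

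| At month 36 | Open arm | Minimally invasive arm | Total |
|---|---|---|---|
| Hazard ratio 1 | 5.8 | 5.8 | 11.5 |
| Hazard ratio 3.74 | 5.8 | 20.8 | 26.6 |

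About 756 × 36/48 = 567 women are randomised by then. A simulated one-sided 0.005 log-rank test at that point (20,000 trials, mean 26.5 events) has about 69% power when the hazard ratio is 3.74. Without a look by arm, 26.6 events at month 36 become 46.6 at month 48, so the 45-event target would be reached about when accrual ends.

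**5. Cost of a harm-only guideline (illustration).** Take one-sided 0.005 at yearly looks from about 15 events. With no true difference, the yearly event counts from year 4 are 20.4, 30.5, 40.4, 50.1, 59.8 and 69.3. Simulating the test statistic at these counts, the chance of at least one false signal is about 1.1% over the three looks before 45 events and about 1.6% through year 9. Stopping for harm can only turn a possible non-inferiority claim into none, so the 2.5% error cannot rise.

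**The case against.** The best defence is that blinded may simply mean coded arms, and that report format and boundaries normally sit in the DMC charter, which is not shown. Much of this stands. The protocol never says the data are pooled, and 1.6 speaks of the DMC observing a difference between groups. Coded arms would serve 1.6 and 7.3. The absence of a numerical boundary from the protocol is not in itself a defect. The charter cannot repair the wording, however. If it provides DFS by named arm, it conflicts with 9.2; if it follows 9.2, the DMC cannot deliver what 7.2 obliges it to do.

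Three stronger readings are tempting but not supported.

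- A reader might infer that the DMC is the sole protection for participants. Section 9.1 lets the Trial Steering Committee terminate the trial and gives it primacy over the DMC, and 9.3.3 and 9.5 allow centres to be closed for poor surgical quality. It remains true that no body is described as seeing DFS by arm.
- A reader might infer from 1.6 that significance would be tested every year at an uncorrected level. No level and no yearly test is stated, and 7.3 says none is planned.
- The usual events formula suggests about 80% power for the month-36 test. It assumes events split evenly between arms; with 79% in one arm, simulation gives about 69%.

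**Conclusion.** The point holds as an internal contradiction. Sections 1.6, 7.2 and 7.3 require action on a comparison of outcomes, and 9.2 withholds either that comparison or its direction. On the pooled reading none of the three duties can be met, because 13.3% pooled events fits both a repeat of LACC and a higher-risk population. On the coded reading only the duty in 7.2 fails. The documents do not show that monitoring fails on every reading.

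The timing figures (about 27 events, roughly 21 against 6, by month 36) and the 69% power rest on exponential DFS, uniform accrual, no dropout and a true hazard ratio of 3.74. The 0.005 level is an illustration and is not in the protocol. The contradiction itself depends on none of these. It bears on participant safety and is cheap to remove, so it should be corrected.

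**What to change.** - **Section 9.2:** replace the blinded-data sentence with a statement that an independent statistician outside the trial team prepares closed reports of DFS by treatment arm for the DMC, and that the sponsor, the Trial Steering Committee and the sites stay blind to comparative results. The trial is open-label, so only the comparison is withheld, not individual allocation.
- **Sections 1.6, 7.2, 7.3 and 9.2:** replace the three triggers with one non-binding, harm-only statistical guideline on DFS. Set its level and timing in the protocol or by explicit reference to the charter.
- **Section 7.3:** state that this is the only comparative look and that there is no early stop for non-inferiority.

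The level is for the sponsor and the DMC to choose. At the illustrative one-sided 0.005 from about 15 events, the false-stop risk with no true difference is about 1.1% up to 45 events (1.6% through year 9), which also bounds the power lost in that case. Beyond that, the cost is a wording amendment, alignment of the charter and one independent report a year.
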